8.2.2. Analysis of Secondary Endpoints

The secondary endpoints for clinical outcomes include the times from randomization to the first occurrence of the adjudicated and confirmed clinical endpoints described below. Time to each of these endpoints will be tested in the FAS with a log rank test stratified by geographic region and complete statin intolerance. For the key secondary endpoints, a fixed sequence testing procedure using the sequence indicated in [Section 4.2](#) will be used with a two-sided alpha of 0.04898. For other secondary endpoints, and for analyses of the key secondary endpoints other than the log rank test, a two-sided $\alpha=0.05$ will be used. A Cox proportional hazards regression model for each endpoint will be fit with treatment group as a covariate and geographic region and complete statin intolerance as stratification factors. If the model fitting fails to converge, complete statin intolerance will be removed as a stratification factor. The hazard ratio and a 95% confidence interval will be reported. The goodness of fit of the Cox proportional hazards regression model for the composite endpoint of cardiovascular death, non-fatal MI or non-fatal stroke will be assessed by visual inspection of Arjas plots. For the key secondary composite endpoint of cardiovascular death, non-fatal MI or non-fatal stroke, and for all-cause death, Kaplan-Meier estimates of time to first event will be plotted.

The reasons for censoring the key secondary composite endpoint of cardiovascular death, non-fatal MI and non-fatal stroke will be summarized by treatment group.

Key secondary endpoints

The key secondary endpoints (as defined in [Appendix 1.2](#)) are the times from randomization to the first adjudicated and confirmed occurrence of:

- A composite endpoint of CV death, non-fatal MI, and non-fatal stroke;
- A composite endpoint of all-cause death, non-fatal MI, and non-fatal stroke, and hospitalization for unstable angina needing urgent revascularization;
- A composite endpoint of all-cause death, non-fatal MI and non-fatal stroke;
- Hospitalization for unstable angina needing urgent revascularization.

Other secondary clinical endpoints

Other clinical secondary endpoints (as defined in [Appendix 1.2](#)) are the times from randomization to first adjudicated and confirmed occurrence of:

- A composite endpoint of CV death, non-fatal MI, non-fatal stroke, and hospitalization for unstable angina;
- CV death;
- Any MI (fatal and non-fatal);
- Fatal MI;
- Non-fatal MI;
- Any stroke (fatal and non-fatal);
- Any stroke (fatal and non-fatal) of any etiology;
- Fatal stroke;
- Non-fatal stroke;
- Hospitalization for unstable angina;
- Hospitalization for congestive heart failure (CHF);
- Any coronary revascularization procedure;
- CABG;

- PCI;
- Any arterial revascularizations;
- All-cause death.

Adjudicated and confirmed causes of all-cause death will be tabulated by treatment group in the FAS. The tabulation will include the event rates and 95% confidence intervals. Causes of all-cause death will be classified according to the Adjudication Committee Charter.

The number and percent of the component that occurs first for the key secondary composite endpoints of cardiovascular death, non-fatal MI or non-fatal stroke will be summarized by treatment group.

Investigator reported potential secondary endpoint events will be listed.

Circulating biomarker secondary endpoints

Percent changes from baseline in all lipid endpoints and hs-CRP and nominal changes from baseline in LDL-C will be analyzed using a mixed model repeated measures (MMRM) model with fixed effects for treatment (categorical variable), scheduled visit time point (categorical variable), baseline value (continuous variable), interaction between baseline value and scheduled visit time point, interaction between treatment and scheduled visit time point, and geographic region (categorical variable), and complete statin intolerance (categorical variable). Observations will be assigned to visits using the analysis windows in [Table 3](#).

Restricted Maximum Likelihood (REML) estimation will be used, and the default covariance structure will be unstructured. Due to the slow onset of accrual in this event-driven trial, there will be few observations at the last several time points. One or more of the last visits may be removed to ensure convergence of the model fitting. Also, the geographic region with the fewest observations may be combined with the next smallest region to ensure convergence of the model fitting. This may be done twice. If the model fails to converge with an unstructured covariance matrix, a spatial power covariance will be used. If the model fails to converge with this covariance structure, compound symmetry will be used. Kenward-Roger degrees of freedom will be used. Consistent with MMRM model fitting, no explicit imputation of missing assessments will be performed. Estimates of treatment group means and mean treatment group differences using observed margins at Week 14 and each other visit, corresponding 95% confidence intervals, and p-values for the mean differences will be provided. The least-squares mean treatment group estimates and 95% confidence intervals will be plotted longitudinally as indicated below with an asterisk (*).

For nominal changes from baseline in Lp(a), triglycerides and hs-CRP, the same model will be fit in the same manner for log-transformed data. The data will be log transformed prior to calculating changes. Any zero values will be replaced with 0.0001 to enable taking the logarithm. The estimated treatment group means using observed margins and corresponding 95% confidence intervals from the analysis of the log-transformed data will be transformed

to percent changes for reporting. The estimated treatment group differences will be transformed to the ratio of the mean percent changes and reported with transformed 95% confidence intervals along with untransformed p-values.

The percent changes from baseline to last non-missing post-baseline measurement in LDL-C will be analyzed using an analysis of covariance model with treatment group and baseline value as covariates and geographic region and complete statin intolerance as factors. Least squares means with corresponding 95% confidence intervals, the least-squares mean differences and corresponding 95% confidence intervals, and p-values will be presented. This analysis will not use analysis windows.

Circulating biomarker endpoints include (asterisk indicates that the LS-mean treatment group estimates and 95% CI will be plotted longitudinally):

- LDL-C*;
- Total cholesterol*;
- HDL-C;
- Triglycerides;
- Non-HDL-C*;
- VLDL-C;
- RLP-C;
- Apo-A-I;
- Apo-B*;
- Lp(a);
- hs-CRP.

8.2.3. Analysis of Safety Data

Safety will be assessed through adverse events (including Type 1 and 3 hypersensitivity reactions and injection site adverse events), serious adverse events, vital signs, examination results (physical and neurologic examinations and cognitive testing), 12-lead ECG recordings, and safety laboratory tests including hematology, blood chemistry studies (including liver function tests and creatine kinase tests), urinalysis studies, and ADA assessments. The Safety Analysis Set (SAS) includes all subjects who have received at least one dose of randomized study medication and will be used for all safety analyses, unless otherwise specified. All summaries of safety data will be descriptive only, unless indicated otherwise.

For summaries by visit, observations will be assigned to visits according to the analysis windows in [Table 4](#).

Adverse Events

The Medical Dictionary for Regulatory Activities (MedDRA) will be used to classify all AEs with respect to system organ class and preferred term. AEs, AEs leading to discontinuation from treatment, and SAEs after the first dose of study medication will be tabulated by treatment group. AEs after the first dose of study medication will be summarized without any requirement that the intensity increase after the first dose of study medication. Summaries will also be provided by severity. Summaries by the relationship to study therapy will be presented for AEs and SAEs only.

In addition, a 3-tier approach will be used. Tier 1 AEs are AEs of special clinical interest, including (but not limited to) Type 1 and Type 3 hypersensitivity reactions and injection site adverse events, and will be specified in the Safety Review Plan. For these events, the number and percentage of subjects with AEs with onset after the first dose of study medication, the risk difference versus placebo, the associated 95% confidence interval, and p-value will be reported. An exact method based on inverting two one-sided tests at half the significance level each (Chan and Zhang, 1999) will be used. The confidence intervals and p-values are not adjusted for multiplicity and are provided for screening purposes only. Tier 2 AEs are those that are not Tier 1, but are common, occurring in $\geq 5\%$ of subjects in any treatment arm. For these events, the number and percentage of subjects with AEs with onset after the first dose of study medication, the risk difference versus placebo and the associated 95% confidence interval will be reported. For these events, the asymptotic method of Miettinen and Nurminen (1985) will be used. The confidence intervals are for estimation purposes only. All events are Tier 3 events and will be summarized as described above.

It should be recognized that this study is not designed to reliably demonstrate a causal relationship between the use of a pharmaceutical product and an adverse event or a group of adverse events. Adverse events in this study are generally not formally adjudicated procedures for the purpose of event classification. Safety analyses are generally considered as exploratory analyses intended to generate hypotheses for further investigation. The 3-tier approach is such an exploratory analysis.

AEs with onset after the first dose of study medication will be tabulated for subjects in subgroups identified in [Section 5.4.2.2](#).

The number and percent of investigator-reported new diagnoses of diabetes with onset after the day of the first dose of study medication will be tabulated by treatment arm in subjects without a baseline history of diabetes.

Injection site adverse events with onset after the day of the first dose of study medication will also be summarized for the bococizumab subjects according to ADA and nAb status.

Vital signs

Observed values and changes from baseline in systolic BP, diastolic BP, PR, and weight will be tabulated by visit as continuous endpoints according to sponsor standards. Height, waist circumference, and temperature will be listed.

Anti-drug antibody (ADA) and neutralizing antibody (nAb)

The number of samples analyzed for ADA and nAb will be summarized.

ADA and nAb status will be summarized as categorical endpoints by visit and overall at the subject level. The numbers and percentages of ADA positive and nAb positive subjects classified according to timing of first result with respect to last dose of bococizumab (on treatment/off treatment) and characterization of ADA and nAb response (treatment induced/treatment boosted/indeterminate) using the definitions in [Section 6.2](#) will be presented.

In addition, the summary of nAb will be repeated with two different denominators: number of non-missing ADA samples and number of ADA positive subjects.

Antibody titers for ADA positive subjects and nAb positive subjects will be summarized by visit as continuous endpoints. Boxplots of ADA titer and nAb titer over time will be presented.

Time to first positive ADA result and time to first positive nAb result will be summarized as continuous endpoints in the subgroups listed [Section 5.4.2.5](#).

Clinical laboratory measurements

Observed values and changes from baseline in hematology, blood chemistry, and quantitative urinalysis parameters will be tabulated by visit as continuous endpoints according to sponsor standards. Mean changes from baseline will be plotted longitudinally for selected laboratory parameters including creatine kinase, hemoglobin, HbA1c and glucose, according to sponsor standards. Qualitative urinalysis parameters will be listed.

Observed value and change from baseline in HbA1c will be tabulated by visit as continuous endpoints for the subgroup identified in [Section 5.4.2.3](#).

Laboratory shift tables for hemoglobin, CK, glucose, and HbA1c will summarize shifts from baseline status (below lower limit of normal, normal, above upper limit of normal) to post-baseline status at each scheduled measurement. Shifts from baseline to the smallest post-baseline and largest post-baseline measurement will also be tabulated. These shift tables will also be done for the subgroups identified in [Section 5.4.2.3](#).

Observations of potential clinical concern after the first dose of study medication for hematology, blood chemistry and all urinalysis parameters will be tabulated by treatment group as categorical variables according to sponsor standards. Subjects meeting one or more criterion for Hy's Law will be tabulated by treatment group according to sponsor standards.

The maximum post-randomization total bilirubin value will be plotted against the maximum post-randomization alanine transaminase (ALT) value (Evaluation of Drug-Induced Serious Hepatotoxicity [eDISH] plot).

Electrocardiograms

12-lead ECGs will be locally read and the interpretations will be kept at the investigation sites as source documents. Any clinically significant ECG abnormalities will be reported as AEs. As a result of the discontinuation of the bococizumab clinical development program, ECG data will not be summarized or listed.

Physical and neurological exams

As a result of the discontinuation of the bococizumab clinical development program, physical examination findings will not be listed. Also, neurological exam findings will not be summarized or listed.

Cognitive Tests

Changes from baseline in cognitive test results, including the Digit Span Forward score, Digit Span Backward Score, Digit Symbol - Coding score, Trail Making A score, Trail Making B score, HVLT Total Recall score, HVLT Delayed Recall Trial score, and the HVLT Recognition score will be analyzed using an MMRM model. The fixed effects will be treatment group (categorical variable), scheduled visit time point (categorical variable), baseline value (continuous variable), interaction between baseline value and scheduled visit time point and interaction between treatment and scheduled visit time point. REML estimation will be used and the default covariance structure will be unstructured. Due to the slow onset of accrual in this event-driven trial, there will be few observations at the last several time points. One or more of the last visits may be removed to ensure convergence of the model fitting. If the model fitting fails to converge, compound symmetry will be used as the covariance structure. Consistent with MMRM model fitting, no explicit imputation of missing assessments will be performed. Estimates of treatment group means and mean treatment group differences at each visit along with corresponding 95% confidence intervals will be provided. The confidence intervals are for estimation purposes only.

Depression assessment

The PHQ-2 score and PHQ-9 score will be summarized by treatment group at baseline as categorical variables according to sponsor standards using the following categories: scores of 0, 1-4, 5-9, 10-14, 15-19, and 20-27, which represent no depression, minimal, mild, moderate, moderately severe, and severe depression, respectively.

8.2.4. Analyses of Other Endpoints

Demographics, alcohol and tobacco use, cardiovascular risk history, medical history, pretreatment and concomitant lipid lowering medications, protocol deviations, compliance with study medication, exposure to study medication, and reasons for discontinuation from treatment and the study will be tabulated by treatment group according to sponsor standards.

The number and percent of subjects with randomized study drug dosing adjustments will be tabulated by treatment group at each visit, as well as at any time during the study. The number and percent of subjects at each dose and regimen will be tabulated by treatment group at each visit. The number and percent of subjects who maintained the dose and regimen from the previous visit and the number who changed the dose and regimen from the previous visit will be tabulated by treatment group for each post-baseline visit after the first visit.

Time from first dose of randomized study medication to premature discontinuation of randomized study medication will be analyzed in the SAS. The p-value from a log rank test stratified by geographic region and complete statin intolerance will be presented. A Cox proportional hazards model will be fit with treatment group as a covariate and geographic region and complete statin intolerance as stratification factors. The hazard ratio and a 95% CI will be presented.

Medication errors and subcutaneous injection site reaction assessments will be listed.

8.2.4.1. Pharmacokinetic/Pharmacodynamic/Immunogenicity Reporting

Pharmacokinetic/Pharmacodynamic (PK/PD) endpoints include plasma bococizumab concentration. Bococizumab blood samples will be collected from all subjects, but only analyzed for bococizumab subjects, if needed, to help understand the PK, PD and safety profile of bococizumab in this study population.

Only plasma samples for all bococizumab-treated subjects will be tested for immunogenicity; plasma samples for placebo-treated subjects will not be tested. Only ADA positive samples will be tested for nAb.

8.2.4.1.1. Definitions

ADA and nAb titers are provided to Pfizer in log₂ format and will be reported in the same manner. All titles and labels used in tables and figures should clearly indicate titer (log₂).

ADA Measurement Level Status:

An ADA measurement is considered as ADA positive if the ADA titer ≥ 6.23 ; otherwise if non-missing, the measurement is considered as ADA negative.

nAb Measurement Level Status:

An nAb measurement is considered as nAb positive if the nAb titer ≥ 1.58 (Assay #2).
An nAb measurement is considered as nAb negative if the ADA measurement from that sample is negative or if the nAb titer < 1.58 .

ADA Subject Level Status – For subject level classification of ADA (positive, negative):

A subject will be considered ADA positive if:

- The subject is ADA negative at baseline and has at least 1 ADA positive post-dose measurement, or
- The subject is missing the baseline ADA measurement and has at least 1 ADA positive post-dose measurement, or
- The subject is ADA positive at baseline and has a >1.58 unit increase in ADA titer from a positive baseline titer in at least 1 post-dose measurement.

A subject will be considered ADA negative if:

- The subject is ADA negative at baseline and all post-dose measurements are negative, or
- The subject is missing the baseline ADA measurement and all post-dose measurements are negative, or
- The subject is ADA positive at baseline but does not experience >1.58 unit increase in titer from a positive baseline titer in any post-dose measurement.

nAb Subject Level Status – For subject level classification for nAb (positive or negative):

A subject will be considered nAb positive if:

- The subject is nAb negative at baseline and has at least 1 nAb positive post-dose measurement, or
- The subject is missing the baseline nAb measurement and has at least 1 nAb positive post-dose measurement, or
- The subject is nAb positive at baseline and has a >1.58 unit increase in nAb titer from a positive baseline titer in at least 1 post-dose measurement.

A subject will be considered nAb negative if:

- The subject is ADA negative, or
- The subject is nAb negative at baseline and all post-dose measurements are nAb negative, or
- The subject is nAb positive at baseline but does not experience a >1.58 unit increase in titer from a positive baseline titer in any post-dose measurement.

ADA (nAb) Response Type:

ADA (nAb) positive subjects will further be classified according to the type of ADA (nAb) response (treatment induced/treatment boosted/indeterminate):

A subject will be considered as having treatment induced ADAs (nAbs) if:

- The subject is ADA (nAb) negative at baseline with at least 1 ADA (nAb) positive post-dose measurement, or
- The subject's baseline ADA (nAb) sample is missing with an ADA (nAb) negative post-dose measurement followed by at least 1 ADA (nAb) positive post-dose measurement.

A subject will be considered as having indeterminate ADAs (nAbs) if:

- The subject's baseline ADA (nAb) sample is missing with at least 1 ADA (nAb) positive post-dose measurement that was not preceded by an ADA (nAb) negative post-dose sample.

A subject will be considered as having treatment boosted ADAs (nAbs) if:

- The subject's baseline sample was ADA (nAb) positive with an increase in ADA (nAb) titer of >1.58 unit increase in titer from a positive baseline titer in at least 1 post-dose measurement.

Timing of ADA (nAb) Positive Measurement:

ADA (nAb) positive subjects will also be classified according to the timing of the ADA (nAb) positive measurement with respect to last dose of bococizumab (on treatment/off treatment):

A subject will be considered as having on-treatment ADAs (nAbs) if:

- The subject has any ADA (nAb) detected within ≤ 14 days after last dose.

A subject will be considered as having off-treatment ADAs (nAbs) if:

- The subject has their first ADA (nAb) detected >14 days after last dose.

Duration of ADA (nAb) Response:

ADA (nAb) positive subjects will also be classified according to the duration of ADA (nAb) response (indeterminate/persistent/transient) if the date of the first post-baseline measurement to the date of the last post-baseline measurement is at least 16 weeks:

A subject will be considered as having indeterminate duration of ADAs (nAbs) if:

- The subject has a positive ADA (or nAb) detected at the last post-baseline time point only

A subject will be considered as having persistent duration of ADA (nAb) if:

- The subject has positive ADA (or nAb) detected at all post-baseline samples assayed during any period of at least 16 weeks

A subject will be considered as having transient duration of ADA (nAb) if:

- The subject has been classified as neither persistent nor indeterminate

ADA (nAb) titer response:

Subjects will also be classified according to their maximum ADA (nAb) titer as

- ADA (nAb) negative,
- Maximum ADA (nAb) titer in the 1st tertile,
- Maximum ADA (nAb) titer in the 2nd tertile, or
- Maximum ADA (nAb) titer in the 3rd tertile.

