- Blood for fasting lipid profile:

Lipid level tests should be scheduled no sooner than 10 days after the subject's prior dose, even if this requires an unscheduled visit;

If a subject has a visit that is scheduled less than 10 days after the last dose, the visit procedures may take place, but lipid testing should be postponed and performed at the earliest possible time, at an unscheduled visit, no sooner than 10 days after the subject's last dose;

- LFTs;
- Blood specimens acquired for ADA, bococizumab level, and PCSK9 level in all subjects at Visit 6 only;

After randomization, if lipid sampling has been postponed to an unscheduled visit, the corresponding ADA/PK/PCSK9 samples should be postponed as well, and collected at the same time as the rescheduled lipid sample collection;

- Urine and serum for pregnancy testing (if indicated).

#### 6.4.3. Visits 8, 9, 10, 12, 13, 15, 16, 18, and 19

At weeks 14, 26, 40, 70, 86, 122, 140, 174, and 192, the following procedures and assessments should be made before subject self-injection:

- **Laboratory test review:** There should be a review of results from laboratory values of the previous visit.
- **Vital signs:** Temperature, PR, and BP will be measured and recorded in the CRF as described in [Section 7.2.3.1](#).
- **Concomitant medications:** Background prescribed lipid lowering treatment (drug name and dose) and all other concomitant treatments will be recorded in the CRF. Instruct subjects on the use of concomitant medications ([Section 5.8](#)).
- **Health care resource utilization:** Assessment of healthcare resource utilization ([Section 7.7](#))
- **Assessment of AEs (including SAEs) or potential CVD outcome events:** Subjects will be asked if any AEs have occurred. AEs (serious and non serious) should be recorded on the CRF. SAEs should be reported as per the safety requirements of the study ([Section 8.6](#)). Subjects should be specifically interrogated with respect to the occurrence of potential outcome events. Potential CVD outcome events should be reported as required ([Section 8.6.1](#)).
- **EQ-5D:** Subjects will complete brief questionnaire as described in [Section 7.3](#) at Visits 8 and 9 only. Results will be transcribed to the CRF.
- **IRT interaction:** At the time of the visit, the visit will be registered in the IRT which will trigger an allocation of IP for the subject.

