- **Investigational product:** Dispense IP based on IRT randomization code. If there is dosing during the visit, subjects will be observed, at the visit, during the injection of IP, either by self-injection, or as performed by a care giver, after all other procedures have been completed.

Subjects will be provided with IP kits to bring home with them and will be reminded about storage conditions.

- **Compliance check:** The subject's compliance with IP administration, as described in [Section 5.3](#), will be assessed. Collect all used and unused syringe cartons in a biohazards container. Subjects will be instructed to bring any used and unused syringe cartons to each visit. Used syringes will be returned to the study center in a biohazard container, when it is full, to receive a new container, and when directed by the study site, as described in [Section 5.3](#). Compliance with lifestyle guidelines should also be reviewed ([Section 4.4](#)) and recorded in the CRF.

- **Contraception check:** At these visits, a contraception check should be made for male and female subjects, who, with their partner, are of childbearing potential ([Section 4.4.2](#)).

The following laboratory tests should be collected:

- Blood for fasting lipid profile;

Lipid level tests should be scheduled no sooner than 10 days after the subject's prior dose, even if this requires an unscheduled visit;

If a subject has a visit that is scheduled less than 10 days after the last dose, the visit procedures may take place, but lipid testing should be postponed and performed at the earliest possible time, at an unscheduled visit, no sooner than 10 days after the subject's last dose;

- Special lipid and efficacy studies, as described in [Section 7.1.2.2](#), will be collected at Week 14, Visit 8.
- Chemistry group;
- LFTs;
- Blood specimens acquired for ADA, bococizumab level, and PCSK9 level in all subjects at Visits 8, 10, and 12;

After randomization, if lipid sampling has been postponed to an unscheduled visit, the corresponding ADA/PK/PCSK9 tests should be postponed as well, and collected at the same time as the rescheduled lipid sample collection;

- Urine and serum for pregnancy testing (if indicated).

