- **IRT interaction:** At the time of the visit, the visit will be registered in the IRT which will trigger an allocation of IP for the subject, except at the EDC or EOS visit. At the EDC or EOS visit, the EDC or EOS status will be registered.
- **Investigational product:** Dispense IP based on IRT randomization code (except for EDC or EOS visit). If there is dosing during the visit, subjects will be observed, at the visit, during the injection of IP, either by self-injection, or as performed by a care giver, after all other procedures have been completed. Except for EDC or EOS visit, subjects will be provided with IP kits to bring home with them and will be reminded about storage conditions.
- **Compliance check:** The subject's compliance with IP administration, as described in [Section 5.3](#), will be assessed. Subjects will be instructed to bring any used and unused syringe cartons to each visit. Used syringes will be returned to the study center in a biohazard container, when it is full, to receive a new container, and when directed by the study site, as described in [Section 5.3](#). Compliance with lifestyle guidelines should also be reviewed ([Section 4.4](#)) and recorded in the CRF.
- **Contraception check:** At these visits, a contraception check should be made for male and female subjects, who, with their partner, are of childbearing potential ([Section 4.4.2](#)).

The following laboratory tests will be collected:

- Blood for fasting lipid profile;

Lipid level tests should be scheduled no sooner than 10 days after the subject's prior dose, even if this requires an unscheduled visit;

If a subject has a visit that is scheduled less than 10 days after the last dose, the visit procedures may take place, but lipid testing should be postponed and performed at the earliest possible time, at an unscheduled visit, no sooner than 10 days after the subject's last dose;

A lipid profile will not be collected at EDC/EOS visits.

- Special lipid and efficacy studies as described in [Section 7.1.2.2](#), at Month 12, Visit 11;
- Biospecimens as described in [Section 7.5](#), at Week 52, Visit 11;

- Chemistry group (including LFTs and CK level);
- Hematology;
- Urinalysis;
- HbA1c for all subjects at Visit 11 and EDC and/or EOS;
- Blood specimens acquired for ADA, bococizumab level, and PCSK9 level in all subjects at Visits 14, 17, 20, and EDC or EOS;

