#### **7.2.7.2. Hypersensitivity Types 1 and 3 Reactions**

Type 1 hypersensitivity or allergic (eg, shortness of breath, urticaria, anaphylaxis, angioedema) reactions are theoretically possible in response to any injected protein. Immune complex mediated Type 3 hypersensitivity reactions are similar to the adverse events (AEs) of Type 1 reactions but are likely to be delayed from the time of injection and may include symptoms such as rash, urticaria, polyarthritis, myalgias, polysynovitis, fever, and, if severe, glomerulonephritis.

In the case of a hypersensitivity reaction, the subject will be treated symptomatically with supportive care, further monitoring, and treatment with anti-histamines and/or corticosteroids. Study injections may be stopped and the subject will be followed until the end of the study. At the time of any hypersensitivity reaction an ADA, PK, and PCSK9 specimen should be collected, and another sample collected at the next visit, as per the [Schedule of Activities](#).

If a subject reports an injection site reaction that has not resolved by the end of the third day, after dosing, an unscheduled visit should be performed, to collect an ADA, PK, and PCSK9 sample.

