8.2.4.5. Injection Site Adverse Events

Injection site adverse events will be summarized by ADA status (positive, negative) and by nAb status (positive, negative). The higher level term of “injection site reactions” will be used to identify the adverse events.

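### ADA samples triggered by reactions count towards an any-positive ADA/nAb status, so AE tables by that status lean towards an association by an amount the plan cannot show

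*SAP*

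**What the plan says.** **Planned draws.** Protocol 6.4.2 has "Blood specimens acquired for ADA, bococizumab level, and PCSK9 level in all subjects at Visit 6 only". Protocol 6.4.3 has "Blood specimens acquired for ADA, bococizumab level, and PCSK9 level in all subjects at Visits 8, 10, and 12". Protocol 6.4.4 has "Blood specimens acquired for ADA, bococizumab level, and PCSK9 level in all subjects at Visits 14, 17, 20, and EDC or EOS". After baseline this means Weeks 4, 14, 40, 70, 104, 156 and 208, plus the early-discontinuation (EDC) or end-of-study (EOS) visit.

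**Triggered draws.** Protocol 7.2.7.2 says "If a subject reports an injection site reaction that has not resolved by the end of the third day, after dosing, an unscheduled visit" is to be made "to collect an ADA, PK, and PCSK9 sample". It also says "At the time of any hypersensitivity reaction an ADA, PK, and PCSK9 specimen should be collected, and another sample collected at the next visit"; that sentence ends by referring to the Schedule of Activities. Protocol 7.2.1.2 has the central laboratory send unscheduled as well as scheduled results to the clinical database.

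**Status rule.** In SAP 8.2.4.1.1 the first route to ADA-positive status is "The subject is ADA negative at baseline and has at least 1 ADA positive post-dose measurement, or". A missing baseline is treated the same way. A positive baseline needs a titre rise above 1.58 log2 units, again in any one post-dose sample. A subject with a negative or missing baseline is ADA negative only if every post-dose result is negative. The nAb rule is parallel. None of these conditions mentions planned visits.

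**Use.** SAP 8.2.4.5 says "Injection site adverse events will be summarized by ADA status (positive, negative) and by nAb status (positive, negative". SAP 5.4.2.2 and 8.2.4.4 do the same for AEs and SAEs. SAP 5.4.2.2 and 5.4.2.3 add a general caution that these subgroups rest on post-randomization data.

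**The concern.** The reaction is the outcome in these tables and ADA status is the grouping variable, but the reaction also changes how often the grouping variable is measured. Under an any-positive rule an extra test can only move a subject from negative to positive. With equal follow-up and no true relation, subjects whose reactions triggered a draw will be called positive more often than the rest.

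Whether antibodies go with injection-site and hypersensitivity reactions is a central safety question for a monoclonal antibody. Only bococizumab samples are assayed (SAP 8.2.4.1), so no placebo table exists in which the artefact would show itself. The general caution does not tell a reader that sampling depended on the reaction.

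**Working it through.** The plan states no figure for this point, so there is nothing to reproduce. The following is an illustration.

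**Input from the documents.** Overall ADA positivity in three earlier studies: 201/473 = 42.5% (Protocol 1.2.3).

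**Assumptions.**
- Reactions are unrelated to ADA (true odds ratio 1).
- k planned post-dose samples per subject, with k = 2 to 5. This fits staggered entry (Protocol 9.1 plans about half of recruitment in the last six months), the stop on 01 November 2016, and the SAP's own expectation of few late observations.
- Results within a subject follow a beta-binomial distribution with mean m and correlation ρ.

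**Formula.** With s = (1−ρ)/ρ and b = (1−m)s, P(all k negative) is the product over j = 0 to k−1 of (b+j)/(s+j). Choose m so that k samples give 42.5% positive, then add the triggered sample.

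**Worked case, k = 3, ρ = 0.5.** Here s = 1, m = 0.270 and b = 0.730.
- Three samples: 0.730 × (1.730/2) × (2.730/3) = 0.575 negative, so 42.5% positive.
- Fourth sample: 0.575 × (3.730/4) = 0.536 negative, so 46.4% positive.
- Odds ratio: (0.464/0.536)/(0.425/0.575) = 1.17.

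**Spurious odds ratio from one extra sample:**

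| k | ρ = 0 | ρ = 0.5 | ρ = 0.8 | ρ = 1 |
|---|---|---|---|---|
| 2 | 1.75 | 1.28 | 1.10 | 1.00 |
| 3 | 1.48 | 1.17 | 1.07 | 1.00 |
| 4 | 1.35 | 1.12 | 1.05 | 1.00 |
| 5 | 1.28 | 1.09 | 1.04 | 1.00 |

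At k = 7 the values for ρ = 0.5 and 0.8 are 1.06 and 1.03. If a hypersensitivity reaction really adds two samples, the range for k = 2 to 5 and ρ = 0.5 to 0.8 is 1.07 to 1.50.

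**Dilution in the injection-site table.** Only reactions that outlast day 3 trigger a draw. Suppose half of the subjects in the table had one (assumption). For k = 4, ρ = 0.8 the positive proportion among reactors is (0.425 + 0.436)/2 = 0.431, an odds ratio of 1.02. For k = 2, ρ = 0.5 it is (0.425 + 0.486)/2 = 0.455, an odds ratio of 1.13.

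**Planned visits only.** With equal follow-up, both groups have the same number of chances, and the sampling-induced odds ratio is 1.00 for every k and ρ.

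**The case against.** The case against rests on size and use, and much of it stands.

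- **Persistence.** Antibody status is not redrawn independently at each visit, and the SAP itself defines a persistent category. A reader might infer odds ratios of 1.3 to 1.8 or more by treating samples as independent (the ρ = 0 column, or two extra samples). The documents do not support independence.
- **The second hypersensitivity sample.** A reader might count two extra samples for every such reaction. Because the sentence refers to the Schedule of Activities, the next-visit sample may be a draw that every subject has.
- **Which tables.** No separate table of hypersensitivity by ADA status is planned. Those events sit within the general AE and SAE tables.
- **Limited use.** SAP 8.2.3 makes safety summaries descriptive unless stated otherwise and calls safety analyses exploratory. No test or odds ratio by ADA status is planned.
- **The other bias.** Dropping triggered samples would place a subject with a confirmed positive at the reaction in the negative column, and could hide a real transient link: planned draws are 26 weeks apart between Weeks 14 and 40. So it does not follow that planned-visit status should replace the any-sample rule.
- **EDC draws.** A reaction may stop injections. Permanent discontinuation brings an EDC visit with its own ADA draw, while later telephone follow-up may remove planned draws. A planned-visit rule therefore does not equalise everything.

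These points limit the size and shape the remedy. They do not remove the mechanism, and the general caution does not name it.

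**Conclusion.** The concern holds as a directional bias of undocumented and probably modest size. Triggered samples count towards a status that turns positive on any one sample, and AEs are then tabulated by that status. For k = 2 to 5 planned samples, 42.5% positivity and ρ = 0.5 to 0.8, one extra sample gives a spurious odds ratio of about 1.04 to 1.28. It is lower in the injection-site table and zero in effect if ADA is fully persistent. Apart from the 42.5%, these inputs are assumptions.

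A reader might go further and infer that the tables must show an association where none exists, or that any association seen is an artefact. Neither follows. The bias arises only through subjects whose sole qualifying positive is a triggered sample, and the documents do not say how many there will be. The tables as planned cannot separate the artefact from a real link; a second version and one count would help to do so.

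**What to change.** 1. Keep the any-sample definition for overall ADA and nAb incidence.
2. For the AE, SAE and injection-site AE tables by ADA/nAb status, add a version with status derived only from the planned ADA visits (Weeks 4, 14, 40, 70, 104, 156, 208). Count draws postponed under the 10-day rule as planned, and exclude samples triggered under Protocol 7.2.7.2.
3. Show that version with and without EDC/EOS draws, because an EDC visit can itself follow a reaction.
4. Report the number of subjects positive only on a triggered sample, and list triggered results beside the reaction. If the number is close to zero, the issue can be set aside.

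The sampling itself need not change. The cost is SAP wording, a few extra tables and a flag for the reason of each draw; an unscheduled flag is not enough, since postponed planned draws are also unscheduled. The downside is that, in the added version, some subjects with a true positive at the reaction count as negative, which is why it stands beside the any-sample version.
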